### [name]

whim of the untrained health promoter or pharmacist. In this way, we anticipate that the risks of applicationguided care will be less than the status quo.

We anticipate that our approach could also be adapted to resource-limited settings around the world, with the potential to extend diabetes and other chronic disease care to patients who do not currently have access to this care due to critical shortages in health system workforce capacity. The knowledge gained by this and subsequent studies to advance this cause warrants the potential risks.

Of the medications we will be utilizing, glibenclamide likely has the highest potential for harm. We did consider using other sulfonylureas which are thought to have a lower risk of hypoglycemia. However, as mentioned in section 2.6, alternate sulfonylureas are not reliably available in Guatemala and/or are prohibitively expensive. In addition, glibenclamide is one of the most widely-used sulfonylureas (and antidiabetic medications in general) worldwide. Thus, the use of glibenclamide in this study may make our approach more generalizable.

We also considered the timing of implementation for dosing changes recommended by the application: in real-time during the visit with retrospective approval by the physician supervisor within 1-2 days or subsequent to physician approval of application recommendations. We ultimately decided that the logistics of requiring physician approval of application recommendations prior to dispensing medications would be prohibitively complicated and would likely lead to patients going without medications for significant periods of time, possibly leading to complications. In essence, the physician has "pre-approved" the medication changes because these are made according to an algorithm designed and tested by physicians and approved by the San Lucas Mission medical director. Additionally, CHWs will be able to consult their coordinator and/or the medical director via telephone at the point of care if there are any questions about medication dosing or other recommendations.

## 2.7.2 Protection Against Risks

The risks of side effects from medications will be mitigated by several mechanisms:

- As decreased renal function increases the risk of adverse effects of metformin and glibenclamide, renal function testing will be required prior to administration of medications for patients with a history of kidney disease and recommended for patients with hypertension and/or duration of diabetes of 10 years or greater. Glibenclamide and metformin will not be used for patients with eGFR <30 mL/min.

- Patients will be asked about adverse effects of metformin monthly. Patients who are taking glibenclamide
  will also be asked about hypoglycemia symptoms and medication will be down-titrated if these symptoms
  are present
- Patients above the age of 65 will have a less stringent treatment goal of A1c ≤8%, in accordance with ADA guidelines.
- Medication will only be up-titrated at 1 month checks when blood glucose is significantly above glycemic goals: FBG >180 mg/dL or PPBG >300 for patients below age 65 and FBG >200 mg/dL or PPBG >300 for patients 65 or older or with multiple comorbidities
- For aspirin use, patients will be asked about history of aspirin allergy in potentially emergent situations (when patient presenting with chest pain that could represent ACS) and aspirin will not be administered to patients with history of allergy. In non-emergent situations, patients will be asked both about history of allergy and signs of GI bleeding (blood in stool or black and tarry stools) prior to dispensing aspirin.

The risks of POC finger stick testing will be minimized by CHW training emphasizing sterile technique and standard precautions.

The risks posed by application malfunction or incorrect use will be mitigated by an intensive alpha testing process (systematically testing each possible scenario prior to implementation with patients to ensure correct

Version #: 1.0

## [name]

recommendations are given in every case), training of CHWs and physician oversight of application treatment recommendations and CHW decisions regarding medication administration and referrals.

Exit criteria for the study includes the following:

- Patient with eGFR <30 mL/min will be unable to safely take metformin or glibenclamide and thus will be
  excluded from the program. These patients will be referred to San Lucas Mission Hospital (SLMH) for
  consultation with [name] regarding alternate medication therapy.

- Women who are found to be pregnant during the study
- Patients who require insulin or additional medication other than metformin or glibenclamide for diabetes control

Patients with mild adverse effects, such as gastrointestinal upset from metformin or mild hypoglycemia or hypoglycemia symptoms on glibenclamide will have their medication adjusted according to the titration algorithms used by the application. Patients who are unable to tolerate metformin or glibenclamide due to adverse effects will be referred to [name] for assessment and further treatment recommendations. Patients with more severe adverse effects, such as severe hypoglycemia (defined as resulting in alteration in mental status and requiring assistance from a CHW) or hypoglycemia not responsive to initial measures in the field will be transferred to SLMH via ambulance for further care.

The program will pay the costs related to ambulance transfer to SLMH and the cost of treatment for medication adverse effects. Patients may incur costs from treatment for other complications of diabetes that fall outside the scope of the program, though this care is highly subsidized through the SLMH.

## 2.7.3 Potential Benefits to the Subjects

The primary potential benefit to patients is improved control of diabetes and avoidance of complications and premature death from this disease. Patients will also receive free medications and diabetes-related tests (blood glucose, A1c, and renal function testing if needed) while they are participating in the study. In addition, monthly visits will be an opportunity for patients to socialize and form supportive relationships with other patients with diabetes in their communities, which may contribute to an improvement in overall health and wellbeing.

# 3 Study Objectives and Purpose

- Primary Objective: Implement a CHW-led diabetes program to improve diabetes care in the rural communities surrounding San Lucas Tolimán, Guatemala
- Primary Objective: To assess the efficacy of CHWs equipped with a smartphone application on improving
  glycemic control in patients living in rural communities in Guatemala
- Secondary Objective: To assess the ability of CHWs equipped with a smartphone application to identify
  potential complications of diabetes in patients living in rural communities in Guatemala
- Secondary Objective: To assess the safety of diabetes medication titration by CHWs equipped with a smartphone application

# 4 Study Design and Endpoints

# 4.1 General Design

Design: This study is a single group, pre-and post-test feasibility/pilot study

The expected duration of subject participation from enrollment to study completion (including follow up) is 12 months

Version #: 1.0

[name]

Summary of trial periods:

- Enrollment: Months 0-6 (enrollment will be rolling)
- Safety analyses will occur on a monthly basis during the trial (evaluation of data from monthly visits)
- Evaluation of endpoints will first occur at 6 months post enrollment (6-12 months after study initiation for most participants). Participants will be followed up to 12 months post enrollment (12-18 months after study initiation for most participants) if possible based on program logistics and funding. Endpoints would again be assessed at that time

## 4.1.1 Primary Study Endpoints

The primary endpoints will be hemoglobin A1c at 6 months and 12 months post-enrollment. This will be analyzed and reported in two ways:

- Mean hemoglobin A1c in the study group compared to mean value at baseline
- Percentage of patients meeting treatment goal for hemoglobin A1c compared to this percentage at baseline. Treatment goal will be A1c ≤7 for most patients, A1c ≤8 for patients age 65 or older or who have 2 or more comorbidities, or other individualized goal for select patients as determined by the medical director ([name])

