- At the enrollment visit, CHWs will use the smartphone application to screen patients for appropriate inclusion in the program, establish glycemic targets, assess current glycemic control with hemoglobin A1c and blood glucose, measure height, weight, blood pressure, and waist circumference, assess for the presence of diabetes complications (diabetic ulcers, angina, diabetic eye disease), administer oral medications (metformin and/or glyburide, known locally by its alternate name glibenclamide) based on a medication dosing algorithm, and provide diabetes self-management education.
- CHWs will meet with patients on a monthly basis to assess medication adherence and for adverse effects, glycemic control (with blood glucose), screen for diabetic complications, refill medications with titration as needed (if experiencing medication adverse effects or blood glucose is significantly above or below treatment goals), and provide further diabetes education. Again, these activities will be guided by the smartphone application. Every 3 months, the monthly visit will also include A1c measurement for a more definitive measurement of diabetes control and to allow for titration of medications. Patients who are identified as having complications or who are not meeting treatment goals despite maximal dosing of metformin and glibenclamide allowed by the algorithm will be referred to SLM medical director [name] for definitive meangement.
- After all visits, including enrollment and monthly visits, [name], in addition to the study investigators, will
  review data for all patients seen, including treatment recommendations made by the application and
  carried out by the CHWs, and make any changes to the treatment plan as needed based on his clinical
  judgement.
- Mean hemoglobin A1c and proportion of patients meeting treatment goals (primary endpoints) will be
  assessed at 6 months and compared to baseline, in addition to a number of secondary endpoints and
  safety measures as described in the relevant sections of this protocol. If possible, patients will also be
  followed out to 12 months with reassessment of primary and secondary endpoints.

Version #: 1.0

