# 8 Study Analysis

### 8.1 Sample Size Determination

For this study, we plan to recruit approximately 150 patients based on the known population of diabetics in the rural communities surrounding San Lucas Tolimán. Of these, we hope to enroll at least 100 patients in the study. Using these numbers, statistical power was calculated using the UCSF online sample size calculators  for a one-group before-after study. The following parameters were used for calculation:

- a = 0.050
- β = 0.200
- SD for outcome = 2.4 (this was the reported pretreatment SD for A1c for a population of 174 indigenous diabetics upon enrollment in a diabetes treatment program in rural Guatemala)
- Within-subject A1c correlation coefficient (rwithin) of 0.928 (this is based on an analysis conducted to determine the accuracy and precision of the A1CNow®+ testing device49, which we are using in our study) Sample size = 100

With this sample size, we will have adequate power to detect an effect size as small as 0.257% A1c and should easily be able to detect more clinically significant differences of 1% A1c or more.

Version #: 1.0

[name]

Another primary outcome will be the proportion of patients meeting treatment goals vs this proportion at baseline. Using the above website, the same parameters for a and  $\beta$ , sample size of 100, and a baseline proportion of patients meeting treatment goals of 13% (this is based on a needs assessment that we conducted as part of this project), we would have 80% power to detect a proportion of 30.2% of patients with good glycemic control (OR 2.896 compared to baseline).

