## 8.2 Statistical Methods

The primary endpoints will be hemoglobin A1c at 6 months and 12 months post-enrollment. This will be analyzed and reported in two ways:

- Mean hemoglobin A1c in the study group compared to mean value at baseline
- Percentage of patients meeting treatment goal for hemoglobin A1c compared to this percentage at baseline. Treatment goal will be A1c ≤7 for most patients, A1c ≤8 for patients age 65 or older or who have 2 or more comorbidities, or other individualized goal for select patients as determined by the medical director ([name])

Secondary endpoints and analyses will include:

- Mean A1c and proportion of patients at goal at 3 months and 9 months.
- Mean FBG at 6 and 12 months compared to baseline value
- Mean BMI at 6 and 12 months compared to baseline
- Mean waist circumference at 6 and 12 months compared to baseline ٠
- Mean blood pressure at 6 and 12 months compared to baseline
- Number and percentage of patients identified as potentially having the following complications: Ischemic chest pain
  - 0
  - 0 Foot ulcers
  - Ophthalmologic complications 0
  - Hypertension 0
- Percentage of patients successfully completing referrals for potential complications
- Number and percentage of patients referred for poor glycemic control or intolerance of diabetic medications and percentage of these patients who complete referral
- Prevalence of adverse effects of metformin and hypoglycemia symptoms throughout the study
- Patient medication adherence throughout the study and at 6 and 12 months compared to baseline (proportion patient reporting each level of adherence)
- CHW compliance with medication recommendations provided by the application (proportion of visits)

Differences in continuous variables (e.g. mean A1c) will be analyzed using paired, 2-tailed t tests. Differences in categorical values (e.g. percentage of patients meeting treatment goal for A1c) will be analyzed using the McNemar test for binary matched-pairs data.

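### Two A1c measures at two time points are all primary, with no testing order, alpha split or success rule, and the only guaranteed time point is labelled interim

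*Combined protocol and SAP*

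**What the plan says.** **Measures and times.** Section 4.1.1, repeated in 8.2, reads: "The primary endpoints will be hemoglobin A1c at 6 months and 12 months post-enrollment". It continues: "This will be analyzed and reported in two ways", meaning the mean against baseline and the percentage at treatment goal against baseline. Section 7.1 also treats both 6 and 12 months as times for the primary endpoints.

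**Tests and alpha.** In 8.2, continuous outcomes "will be analyzed using paired, 2-tailed t tests", and categorical outcomes use the McNemar test. Section 8.2 gives no significance level. Alpha of 0.05 appears in 8.1, first for mean A1c. The section then says "Another primary outcome will be the proportion of patients meeting treatment goals vs this proportion at baseline" and powers that outcome as well: "Using the above website, the same parameters for a and" beta.

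**Which time point decides.** The overview in 2.1 assesses mean A1c and proportion at goal, both called primary, at 6 months. If possible, patients are then "followed out to 12 months with reassessment of primary and secondary endpoints". Section 4.1 makes follow-up to 12 months conditional: "if possible based on program logistics and funding". Section 7.4.4 guarantees at least 6 months for everyone, makes 12 months depend on funding, personnel and the local partners, and calls the 6-month efficacy analysis interim.

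No section ranks the four comparisons, divides alpha among them, or says which result answers the efficacy objective in section 3.

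**The concern.** A reader of the final report needs to know which result answers the efficacy objective. The plan offers four candidates and no way to choose between them. The two measures need not agree. A patient whose A1c falls from 12 to 9 lowers the mean but does not reach goal, so the mean could improve clearly while percent at goal barely moves.

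The time points are also described inconsistently. Under 2.1, 6 months is decisive and 12 months is a repeat. Under 4.1.1, 7.1 and 8.2 the two are equal. Under 7.4.4 the 6-month analysis is interim, which implies that the final analysis comes later. If follow-up ends at 6 months, the only efficacy result will be one that the protocol labels interim. What is at stake is how the result is interpreted, together with an error rate above 5% if any one of several significant results is presented as the primary finding.

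**Working it through.** **1. The plan's own figure.** Inputs from 8.1: SD 2.4, within-subject correlation 0.928, n = 100, alpha 0.05, beta 0.20.

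- SD of change = 2.4 × √(2 × (1 − 0.928)) = 0.911.
- Detectable change for a two-sided paired t test with 99 df = 0.258 (normal approximation 0.255). The plan states 0.257.
- Power at 0.257 = 79.8%.

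The stated figure reproduces, and it uses the full 0.05 for mean A1c. For percent at goal, 8.1 again uses 0.05 to reach its detectable proportion of 30.2% from 13%.

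**2. Number of primary comparisons.** Two measures × two time points = four. If follow-up stops at 6 months, two remain.

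**3. Chance of at least one false positive if each is tested at two-sided 0.05.** This level is inferred from 8.1.

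| Comparisons | Independent tests | Correlated normal test statistics (assumed r) |
|---|---|---|
| Four | 1 − 0.95⁴ = 18.5% | 16.1% (0.5 between times, 0.5 between measures); 14.8% (0.5, 0.7); 13.7% (0.7, 0.7) |
| Two, at 6 months | 1 − 0.95² = 9.75% | 9.1% (0.5 between measures); 8.3% (0.7) |

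The documents give no correlation between the test statistics, so 0.5-0.7 is an assumed range. A separate patient-level simulation used n = 100, normal data, 13% at goal, and equal correlations of 0.3 to 0.928 among baseline, 6 and 12 months. It gave 15.6% to 16.7% for four tests and 8.5% to 9.4% for the 6-month pair. The 3-month look at the primary endpoints in 8.4 is not counted.

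**4. What control would cost on the plan's inputs.**

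| Approach | Alpha for mean A1c at 6 months | Detectable change | Power at 0.257 | N for 80% power at 0.257 |
|---|---|---|---|---|
| Fixed order, mean A1c at 6 months first | 0.05 | 0.258 | 79.8% | about 100 |
| Bonferroni over two tests | 0.025 | 0.284 | 70.7% | 122 |
| Bonferroni over four tests | 0.0125 | 0.309 | 61.0% | 144 |

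A fixed order limits the error over the two 6-month tests to 5% and leaves the first test as the plan powered it.

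**The case against.** The strongest reply is that this is a single-group feasibility and pilot study feeding a quality improvement process. Both measures summarise one variable, and the plan says both will be reported. Strict control of the familywise error rate belongs to confirmatory trials. Multiplicity would also seldom change the conclusion: even with alpha split four ways the detectable change is 0.309, against the 1% that 8.1 calls clinically significant. With an assumed within-subject correlation of only 0.3 it is 0.96, still below 1%.

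Much of this stands, and it limits how serious the point is. It does not remove it. Section 3 makes efficacy on glycemic control a primary objective, 8.1 powers formal tests of it, and the conflict over which time point is decisive remains whatever the error rate.

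A reader might infer several stronger things that the documents do not support:

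- *That the existence of any primary result depends on funding.* Section 7.4.4 follows every patient to at least 6 months, so a 6-month primary result is planned in any case. Only the 12-month repeat is at risk.
- *That the plan allows success to be declared on any one of four tests.* It contains no success rule of any kind. The gap is the absence of a rule.
- *That the plan states a 0.05 test for each of the four.* Section 8.1 has two power calculations, neither tied to a time point, and 8.2 gives no level.
- *That continuation to 12 months will be decided on the 6-month result.* The conditions given in 4.1 and 7.4.4 are logistics, funding, personnel and local partners. Enrollment rolls over months 0-6, so the earliest patients reach 12 months about when the last reach 6. Section 5.7.1 does list efficacy and futility as general grounds for stopping, without boundaries, but it does not link them to the 12-month extension.

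**Conclusion.** The point holds as a gap in specification, with a moderate effect on error. The plan has four co-equal primary comparisons and no order, alpha split or success rule, and its sections disagree on whether 6 months is the primary or an interim assessment. If all four are tested at 0.05, the false-positive chance is 18.5% under independence and about 14-16% under the assumed correlations. For the two guaranteed 6-month tests it is about 8-10%. These figures rest on the inferred 0.05 level and on correlations that the documents do not supply. The point should be settled before the 6-month data are analysed. It does not invalidate the study.

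**What to change.** In 4.1.1 and 8.2:

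1. Make 6 months the primary time point, as in 2.1.
2. Test change in mean A1c at 6 months first, at two-sided 0.05, and state that level in 8.2.
3. Test percent at goal at 6 months, also at 0.05, only if the first test is significant.
4. List both 12-month measures as secondary.

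Align the other sections: 7.1, which gives 6 and 12 months as the primary times; 7.4.4, which calls the 6-month efficacy analysis interim; and 8.1, which says "Another primary outcome will be the proportion of patients meeting treatment goals".

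The cost is wording only. N, alpha and the stated detectable change of 0.257 stay as they are, and all data are still collected and reported. There is a real downside. Sections 2.1 and 8.1 treat percent at goal as primary, so the ordering departs from them on the measure while agreeing with 2.1 on the time point. Under the fix neither percent at goal nor the 12-month results can carry the efficacy claim alone. If the investigators want both measures to remain primary, they could split alpha at 6 months. On the plan's inputs that raises the detectable mean change to 0.284, or needs 122 patients to keep 80% power at 0.257. They could instead require both measures to succeed. Either choice should be written down.

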In order to inform the development of the smartphone application and program protocols, we conducted a community needs assessment during the summer of 2016. Clinical data was used to provide a baseline estimate of diabetes prevalence and distribution in the communities as well as demographic risk factors. Interviews were conducted with local physicians, CHWs, and managers of the CHW system to understand current methods of diabetes treatment and define the limitations of these systems. Out of the 119 patients currently diagnosed with diabetes in the rural communities, 31 were interviewed to illuminate how the disease is currently diagnosed and treated, the effect the disease has on patient lifestyles, and patients' desired attributes for a diabetes treatment program. Finally, we visited local diabetes clinics to determine the current state of diabetes treatment, the availability of medications and resources, and the level of care provided to patients.

Key findings of the community needs assessment were as follows:

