## [name]

- Patients with diabetes in the rural communities have poor access to quality diabetes care. Only 58% of patients are taking medication on a regular basis and only 13% have achieved good glycemic control
- 2. Outreach clinics run by CHWs are disorganized, undersupplied, sporadic, and ineffective
- CHWs lack the experience and training to effectively titrate oral diabetes medications, assess for possible complications, and provide health education for patients
- 4. Patients lack basic diabetes knowledge, particularly regarding self-management

Utilizing the knowledge gained with this needs assessment, established treatment guidelines for diabetes, and the expertise of SLM medical director [name] and the coordinators the SLM CHW program, we developed protocols for the diabetes program, including a smartphone application to allow for algorithmic management. This process was iterative and collaborative and involved our local partners at every step.

In February and March, we trained a group of 10 CHWs, including 5 CHW coordinators (who have more clinical experience and take on a supervisory and training role for less-experienced CHWs) in the basics of diabetes management, program protocols, and the use of the smartphone application we had developed. With close physician supervision, we then beta-tested the use of the application with a small group of patients. Based on this experience, we have further refined the application and program protocols. We now endeavor to implement this program on a wide scale in the San Lucas area to both improve access to care for patients with diabetes and to establish the efficacy, feasibility, and safety of CHW-led, smartphone application-guided diabetes treatment.

CHW training, program protocols, and the algorithmic approaches facilitated by the smartphone application will be described in more detail in the relevant sections of this protocol and its appendices. An overview of study activities is as follows:

- We will train additional CHWs in basic diabetes care, use of point-of-care (POC) testing technology, and use of the smartphone application that will guide their management of patients with diabetes.
- CHWs will recruit patients with diabetes in the rural villages outside of San Lucas to participate in the program.

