# 5.3 Exclusion Criteria

Exclusion Criteria		
1.	Type 1 diabetes	
2.	Women who are pregnant	
3.	Current use of insulin	
4.	Renal insufficiency (eGRF <30 mL/min/1.73 m 	
5.	Unable to provide informed consent	

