# 5.4 Subject Screening for Recruitment

## 5.4.1 Subject Identification

Potential subjects will be identified by CHWs from their prior knowledge of individuals with diabetes in their communities. We also anticipate that study participation will be bolstered by word of mouth communication between patients in the communities. Patients may also be identified during mobile medical clinics run by visiting medical volunteers.

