# 9 Data Collection, Handling and Record Keeping

## 9.1 Data Confidentiality

A service known as CommCare is being used to collect data. Whenever data is transmitted between one of the servers CommCare uses and the Android application, it is sent using HTTPS. Here are the standards incorporated;

- Encrypted server-client connections using HTTPS
- All access to the cloud infrastructure is protected behind a firewall and require unique VPN access permissions
- Data is transferred through channels monitored by intrusion monitoring systems
- Encrypted at-rest database and encrypted database backups every night
- Security management meets ISO 27001, PCI-DSS, SOC1, SOC2, SOC3, and HIPAA standards

The devices used to collect data are encrypted Android smartphones. The CommCare mobile application itself is password protected and data collected by the application is encrypted (AES 256-Bit Symmetric Encyption, fully HIPAA compliant). These are only connected to the internet when data is being uploaded via a WIFI connection. Currently the devices are only being used by the health promoters the days of the diabetes checks, which is usually just 2 or 3 days per month. As soon as all the checks have been completed the devices are returned to the health promoter main building where the data is sent using a WIFI connection and then erased from the device.

The data is stored with other hospital system data used in monitoring an infant nutrition program in a HIPAA compliant server (see above). This data essentially constitutes an aspect of the patient's medical record at the San Lucas Mission Hospital. Persons with access to this database will include SLM medical director [name], the coordinators of the CHW program, [name] (onsite data manager and software engineer), [name] (the PI), and [name] (co-investigator).

Any hard copies of study data will be stored in locked filing cabinets at CHW headquarters in Quixaya and/or San Lucas Mission Hospital. When not in use, smartphones will be stored in a locked cabinet at CHW headquarters in Quixaya.

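### Patients already treated with the application in the beta test can enroll, and their enrollment A1c would then serve as a baseline that is not pre-program

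*Combined protocol and SAP*

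**What the plan says.** The design is one group measured before and after, with no concurrent control (section 4.1). Section 4.1.1 names two primary measures. One is "Mean hemoglobin A1c in the study group compared to mean value at baseline"; the other is the percentage of patients at their A1c goal against that percentage at baseline. Section 8.2 repeats both and gives the tests: "Differences in continuous variables (e.g. mean A1c) will be analyzed using paired, 2-tailed t tests", with McNemar's test for the percentage at goal. Sections 7.1 and 7.4.1 place the baseline A1c at the enrollment visit.

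Section 2.1 reports that, after a first group of CHWs was trained, "we then beta-tested the use of the application with a small group of patients". This was done under close physician supervision, and the application and protocols were revised afterwards. The protocol does not give the number of patients, their A1c values, or whether their treatment continued.

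The only exclusion in section 5.3 that concerns earlier treatment is "Current use of insulin". Section 5.2 asks only for a prior type 2 diagnosis, and section 6.7 accepts patients already on metformin or glibenclamide. On recruitment, section 5.4.1 states: "Potential subjects will be identified by CHWs from their prior knowledge of individuals with diabetes in their communities". Section 8.3 analyses every enrolled patient to the extent of participation and defines subgroups only by baseline A1c. Appendices 1 and 3 ask about diagnosis, history, medication and adherence, but not about earlier care under the application.

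**The concern.** With no control group, the enrollment value carries the whole comparison: it stands for each patient's state before the program. The hypothesis in section 2.2 is about what implementing the program does to glycemic control. A patient managed with the application during the beta test has already received some form of that program. If that care lowered the patient's A1c and the gain lasted, part of the effect sits in the baseline and is subtracted out.

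The percentage at goal is affected in the same way. The 13% used for sizing in section 8.1 comes from a needs assessment made before the application existed, whereas beta-test patients could already be at goal because of the program. They could also enter the planned subgroup of patients at goal at baseline for that reason.

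The plan pools these patients with everyone else, and nothing on its enrollment forms would let an analyst separate them later.

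**Working it through.** **1. Reproduce the plan's figures.** Inputs from section 8.1: "SD for outcome = 2.4", within-subject correlation 0.928, n = 100, alpha 0.05, power 80%. Section 8.2 makes the test two-sided.
- SD of change = 2.4 × √(2 × (1 − 0.928)) = 0.911.
- Detectable change = (1.960 + 0.842) × 0.911 / √100 = 0.255 by the normal approximation, and 0.258 by the noncentral t. The plan states 0.257, where power is 79.8%.
- For 13% versus 30.2%, the odds ratio is (0.302/0.698)/(0.13/0.87) = 2.896, and a continuity-corrected two-proportion formula returns n = 100. Both agree with section 8.1. The planned test is McNemar's, so below I use only the size of this difference, not its power.

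The plan's arithmetic is not at fault.

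**2. Dilution.** Let D be the true full change, f the share of analysed patients who were in the beta test, and q the fraction of D they had already reached at enrollment. They have (1 − q)D left to gain; the others gain D. So:

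observed change = (1 − f)D + f(1 − q)D = D(1 − fq), and dilution = f × q × D.

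The documents give neither f nor q. I assume f = 5%, 10% and 20%, and q = 0.5 and 1. For the goal endpoint with q = 1, baseline = 13% + f × 17.2 points and follow-up is 30.2%.

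| f | Observed change, D = 1, q = 0.5 | Observed change, D = 1, q = 1 | Baseline at goal, q = 1 | Difference (planned 17.2 points) |
|---|---|---|---|---|
| 5% | 0.975 | 0.95 | 13.9% | 16.3 |
| 10% | 0.95 | 0.90 | 14.7% | 15.5 |
| 20% | 0.90 | 0.80 | 16.4% | 13.8 |

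**3. Does the test conclusion change?**
- At D = 1, the size section 8.1 calls more clinically significant, power stays at about 100% in every row.
- That does not hang on the high correlation. With r = 0.5 instead, the SD of change is 2.4, and power at D = 1 is 98.5% undiluted, 96% at f = 10% and 91% at f = 20% (q = 1, ignoring the small added mixture variance).
- Only at the detection limit, D = 0.257 with q = 1, does power fall noticeably: from 79.8% to about 76%, 71% and 60%.

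**4. Leaving the patients out.** With n = 95, 90 and 80, the detectable change is 0.264, 0.272 and 0.289, and power for 0.257 is 77.7%, 75.4% and 70.3%. Keeping them gives 75.5%, 70.7% and 60.3% if q = 1, but 77.7%, 75.6% and 70.9% if q = 0.5. Whether exclusion gains power therefore depends on q.

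**5. How plausible is enrollment?** Section 2.1 states: "Out of the 119 patients currently diagnosed with diabetes in the rural communities, 31 were interviewed". The target of at least 100 is 100/119 = 84% of that pool. Section 8.1 works from about 150, which gives 100/150 = 67%. Either share is large enough that some beta-test patients could enroll, but neither shows that they will.

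**The case against.** The strongest reply is that every step from permitted to biased is conditional. Beta-test patients must enroll, the beta test must have lowered their A1c, and the gain must have lasted to enrollment. The documents state none of these. The group is described as small, it used an application that was later revised, and close physician supervision may not resemble the study program. All of this stands, and it is why the sizes above are a range under assumptions.

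It is also fair that baseline was never meant to be untreated. Section 6.7 expects prior users of both drugs, and section 2.1 says 58% take medication regularly. The problem is narrower: usual care before enrollment is the intended comparator, and care under the application is not.

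Section 9.1 says "Currently the devices are only being used by the health promoters the days of the diabetes checks". A reader might take this as proof that patients were being treated before enrollment. It could equally describe study visits, and I place no weight on it.

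Finally, this dilution works against the program, so by itself it cannot create a false claim of benefit, and this is a feasibility pilot. That limits the seriousness. It does not help the estimate, which serves a primary objective in section 3.

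**Conclusion.** The gap is real: the plan admits beta-test patients, takes their enrollment A1c as baseline, pools them, and has no enrollment item to identify them. If any enroll with a lasting improvement, both primary contrasts can be diluted by f × q × D. Under assumed shares of 5% to 20% with the full effect already reached, that is 0.05 to 0.20 points on a true 1-point fall, and a goal difference of 16.3 to 13.8 points instead of 17.2. At q = 0.5 the A1c figures halve, and a negligible beta group means negligible dilution. What is at risk is the size and meaning of the estimate, not the test result at 1 point.

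Four stronger readings are not supported:
- **The reported change is certainly biased toward zero.** The conditions are unstated. Regression to the mean and the restriction to patients with completed follow-up (section 9.2.2.1) may act the other way, so the net direction is not established.
- **The study loses material power.** This is so only near 0.257, with nearly all the effect reached before baseline.
- **Excluding these patients always costs less power than keeping them.** At q = 0.5 it does not.
- **The safety data come from patients selected for tolerating the program.** No section says so.

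**What to change.** Add one yes/no item to the enrollment form: has this patient previously been treated by a CHW using the application? It must be in place before enrollment starts, because the current questions cannot recover the answer.

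In sections 4.1.1 and 8.3, state that both primary A1c comparisons will also be reported without patients who answer yes, that their number will be given, and that their results will be shown separately. If the sponsor prefers, the primary comparisons can instead be restricted to application-naive patients. That choice should be written down before any follow-up A1c is analysed.

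The cost is one question, one extra analysis and a slightly smaller n in that analysis: for example, n = 90 moves the detectable change from 0.258 to 0.272 on the plan's own inputs. Eligibility and care are unchanged.
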